7.6.4 Review of Adverse Event Rates

If an increase in the frequency of Grade 3 or 4 adverse events (above the rate reported in the Investigator Brochure or package insert) is noted in the study, a report should be submitted to the DSMC at the time the increased rate is identified. The report will indicate if the incidence of adverse events observed in the study is above the range stated in the Investigator Brochure or package insert.

If at any time the Investigator stops enrollment or stops the study due to safety issues, the DSMC Chair and DSMC Manager must be notified within 1 business day via e-mail. The DSMC must receive a formal letter within 10 business days and the CHR must be notified.

Data and Safety Monitoring Committee Contacts:

DSMC Chair:

Phone:

Email:

Address:

UCSF
San Francisco, CA 94115

DSMC Monitors

[REDACTED]
UCSF Helen Diller Family
Comprehensive Cancer Center
San Francisco, CA 94115

8.1 Identification

Ipilimumab is available in concentrations of 5 mg/mL (50 mg/10 mL and 200 mg/40 mL). The sterile solution in the vial is clear and colorless. Ipilimumab is administered via intravenous infusion only.

8.2 Packaging and Labeling

BMS will provide ipilimumab at no cost for this study. Ipilimumab will be provided in open-label containers. The labels will contain the protocol prefix, batch number, content, storage conditions, and dispensing instructions along with the Investigational New Drug (IND) caution statement.

8.3 Storage, Handling, and Dispensing

8.3.1 Storage

Ipilimumab must be stored in a secure area according to local regulations. The investigator must ensure that it is stored at a temperature $\geq 2^{\circ}\text{C}$ and $\leq 8^{\circ}\text{C}$.

8.3.2 Handling and Disposal

As with all injectable drugs, care should be taken when handling and preparing ipilimumab. Whenever possible, ipilimumab should be prepared in a laminar flow hood or safety cabinet using standard precautions for the safe handling of intravenous agents applying aseptic technique. Latex gloves are required. If ipilimumab concentrate or solution comes in contact with skin or mucosa, immediately and thoroughly wash with soap and water. After final drug reconciliation, unused ipilimumab solution should be disposed at the site following procedures for the disposal of anticancer drugs.

8.3.3 Dispensing

It is the responsibility of the investigator to ensure that ipilimumab is only dispensed to study subjects. The ipilimumab must be dispensed only from official study sites by authorized personnel according to local regulations.

8.4 Drug Ordering and Accountability

8.4.1 Initial Orders

Following submission and approval of the required regulatory documents, a supply of ipilimumab may be ordered from BMS. Investigators must complete a Drug Request Form and email it to: [contact].

If for any reason the e-mail drug request form is not successfully transmitted, contact [REDACTED] Fisher Clinical Services:

www.fisherclinicalservices.com

It is recommended you send a test message to the Fisher Clinical Service e-mail address upon receipt of the Drug Request Form. Please include in the subject line: "BMS IST Drug Order -- Test." This will ensure your site is recognized by Fisher and your future orders will be received without incident.

Ipilimumab vials (40 mL) are shipped in quantities of five. The initial order should be limited to 25 vials (5 cartons of 5 vials each). Allow 5 business days for shipment of drug from BMS receipt of the Drug Request Form. Drug is protocol specific, but not patient specific. All product will be shipped via Federal Express in a temperature-controlled container. Shipments will be made from Fisher Clinical Services on Monday through Thursday for delivery onsite Tuesday through Friday. There will be no weekend or holiday delivery of drugs.

It is possible that sites may have more than one ipilimumab clinical study ongoing at the same time. **It is imperative that only product designated for this protocol number be used for this study.** To help segregate product for this study from other investigational or marketed product, stickers bearing the BMS protocol number will be provided and should be affixed to the front of the outer carton just above the company names so as not to obscure any marking.

8.4.2 Re-Supply

Reorders should be emailed directly to Fisher Clinical Services

[REDACTED] for shipment within 5 business days. When assessing need for resupply, institutions should keep in mind the number of vials used per treatment dose, and that shipments may take 5 business days from BMS receipt of request. Drug is not patient specific. Be sure to check with your pharmacy regarding existing investigational stock to assure optimal use of drug on hand.

8.5 Ipilimumab Accountability

It is the responsibility of the investigator to ensure that a current record of ipilimumab disposition is maintained at each study site where ipilimumab is inventoried and disposed. Records or logs must comply with applicable regulations and guidelines, and should include:

- Amount received and placed in storage area.
- Amount currently in storage area.
- Label ID number or batch number and use date or expiry date.
- Dates and initials of person responsible for each ipilimumab inventory entry/movement.
- Amount dispensed to and returned by each subject, including unique subject identifiers.
- Amount transferred to another area/site for dispensing or storage.
- Non-study disposition (e.g., lost, wasted, broken).
- Amount destroyed at study site.

8.6 Ipilimumab Destruction

If ipilimumab is to be destroyed on site, it is the investigator's responsibility to ensure that arrangements have been made for disposal and that procedures for proper disposal have been established according to applicable regulations, guidelines, and institutional procedures.

Appropriate records of the disposal must be maintained.

9 STATISTICAL METHODOLOGY

9.1 Sample Size Considerations

9.1.1 Safety Lead-in

Six patients at the 3 mg/kg dose of ipilimumab will be randomized to Arm 1 and 2, immediate versus delayed ipilimumab after 4 doses of SipT. If DLTs are encountered as defined above (Section 3.1), then one or both arms may be discontinued. 6 patients will be required to complete this phase of the study.

9.1.2 Phase 2

Primary Immune Objective: This is a multicenter non-comparative randomized Phase 2 trial with the primary objective of immunologic efficacy in addition to safety. Immune response is defined as an IgG antibody response to either PAP or PA2024 by study week 20. The IgG antibody response will be determined with an ELISA assay with a positive response defined as titer > 1:400. To achieve a 40% immune response rate indicating immune activity versus a null hypothesis of 15% indicating lack of immune activity assuming a 2-sided type I error of 5% and 81% power will require 27 total patients per arm. This is based upon the exact binomial test for a single sample. The null hypothesis of 15% is based off an observed anti-PAP IgG response rate of 17.7% seen at a similar time interval in patients treated with sipuleucel-T in the three phase 3 clinical trials⁴⁶. Therefore, an additional 21 patients beyond the safety lead-in phase will be accrued to each arm (an additional 42 patients). The total number of evaluable patients for the Phase 2 study will be 54 patients with accrual up to 66 patients possible. Patients will be accrued at UCSF and MDACC with the randomization to ipilimumab timing stratified by institution.

Secondary Immune Objectives: The sample size with 27 patients in each arm is sufficient to detect a mean difference between the two study arms in immune modulation, a secondary objective, for an effect size (standardized unit) of at least 0.69 for normally distributed variables. Similarly, the sample size is sufficient to detect at least a 37% difference between the two treatment groups in proportions of patients displaying a specific outcome using Fisher's exact test (e.g. 33% versus 70% achieving a certain change in an immune parameter). For both types of tests a level of significance of 0.05 for a directional test and power of at least 0.80 is assumed. Directional tests will be performed to test for an effect due to the timing of ipilimumab. A directional test is being used because a greater immune effect is expected with immediate administration of ipilimumab.

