**CC# 12557: A RANDOMIZED PHASE 2 TRIAL OF IMMEDIATE VS. DELAYED
ANTI-CTLA4 BLOCKADE FOLLOWING SIPULEUCEL-T TREATMENT FOR
PROSTATE CANCER IMMUNOTHERAPY**

[BMS PROTOCOL NUMBER: CA184-175]

Investigational Agent: Ipilimumab (NSC #732442)

IND: IND Exempt (116867)

Protocol Number: CC#12557

Protocol Version: 5.4

Version Date: 08/07/2019

Principal Investigator: [name]

Associate Professor of Medicine in Residence

UCSF Helen Diller Family Comprehensive Cancer Center

Co-Principal Investigator: [name], PhD

Associate Professor

The University of Texas MD Anderson Cancer Center

Department of Genitourinary Medical Oncology

UCSF Co-Investigators:

[name].,

Assistant Clinical Professor of Medicine

[name].,

HS Assistant Clinical Professor

[name].,

HS Assistant Clinical Professor

[name].,

HS Clinical Instructor

[name].,

Professor of Medicine and Urology

[name].

Biostatistician

[name].,

HS Assistant Clinical Professor

MD Anderson Co-Investigator: [name]., Professor of Medicine

Revision History

August 7th, 2019, Version 5.4

February 27, 2014 Version 4.0

January 9, 2019, Version 5.3

November 4, 2013 Version 3.0

November 17, 2016 Version 5.2

August 12, 2012 Version 2.0

March 21, 2016 Version 5.1

May 29, 2012 Version 1.0

October 7, 2014 Version 5.0
March 26, 2014 Version 4.1

PROTOCOL SYNOPSIS

Study Objectives Phase II Study

Primary

- Determine whether the timing of ipilimumab administration impacts PAP and PA2024-specific immune responses induced by SipT.

Secondary

- Assess the safety associated with giving ipilimumab either immediately following completion of Sipuleucel-T (SipT) or delayed ipilimumab following SipT.
- Assess clinical activity of the combination therapy for each study arm in chemotherapy-naïve patients with metastatic CRPC.
- Determine whether the timing of ipilimumab administration impacts the immunomodulation of activated effector and regulatory T cells.

Study Design

This is a non-comparative open-label randomized multicenter Phase 2 clinical trial combining SipT with ipilimumab in patients with chemotherapy-naïve metastatic CRPC.

All patients will be treated with the fixed treatment backbone of SipT (Q2 wks x 3). Patients will be randomized to one of two arms:

Arm 1 (Immediate Treatment):

Ipilimumab Q3 wks x 4 started 1 day following the final dose of SipT (Day 0).

Arm 2 (Delayed Treatment):

Ipilimumab Q3 wks x 4 started 3 weeks following the final dose of SipT (Day 0).

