1 INTRODUCTION

This is a non-comparative open-label randomized phase 2 study to treat patients with chemotherapy-naïve, metastatic CRPC with standard sipuleucel-T (SipT) of 3 treatments Q2 wks. Subjects will then initiate ipilimumab treatment (Q3 wks x 4 doses) either 1 day following the last dose of SipT (immediate arm) or 3 wks following the last dose of SipT (delayed arm) until disease progression or toxicity. Subjects will receive ipilimumab at the 3 mg/kg dose. Twenty-seven evaluable patients will be required per treatment arm, and a total of 54-86 prostate cancer patients will be required to complete this multicenter study. The study will assess immunologic activity of immediate ipilimumab administration following SipT treatment and delayed ipilimumab administration following SipT as measured by immune responses to prostatic acid phosphatase (PAP) and the PAP- GM-CSF fusion protein (PA2024). The latter is the antigen used in producing SipT.

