1.1 Research Hypothesis

We hypothesize that combining Sipuleucel T with ipilimumab will enhance the immunogenicity and clinical efficacy as determined by PSA decline and time to progression of this treatment. We also hypothesize that potentiation of PAP-specific T cell responses will be dependent on timing of anti-CTLA-4 administration in relationship to last dose of sipuleucel-T (SipT).

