2 STUDY OBJECTIVES: PHASE II STUDY

2.1 Primary Objective

- Determine whether the timing of ipilimumab administration impacts PAP and PA2024-specific immune responses induced by SipT.

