9.3 Methods for Analysis

9.3.1 Primary Endpoints

9.3.1.1 *Safety Lead-in: Assess the safety of combining ipilimumab with SipT.*

Toxicities will be reported for each study arm at each dose of ipilimumab administered with descriptive statistics (e.g. proportions) by tabulating the frequency of the maximum grade occurring for each patient for each type using NCI CTC v. 4.0 criteria. As described above the type and grade of all such IraEs will be tabulated by treatment arm. Toxicity results will be presented indicating occurrences during the first 20 weeks of protocol therapy and those occurring later.

9.3.1.2 *Phase 2: Determine whether the timing of ipilimumab administration impacts PAP and PA2024 specific immune responses by SipT*

The primary immune study hypothesis to assess the frequency of observing an immune response to PAP and/or PA2024 by week 20, when the induction ipilimumab therapy is completed, for each of the two ipilimumab schedules will be tested using the single sample binomial exact test. The IgM and IgG antibody responses to PAP and PA2024 will be assessed with an ELISA assay at baseline and week 20 after the start of sipT treatment (day 113 of study treatment). A positive response will be defined as a titer > 1:400. The primary hypothesis will be tested by comparing the proportion of patients achieving an IgG immune response to PAP or PA2024 to the null hypothesis of 15% (based off an observed anti-PAP IgG response rate of 17.7% seen at a similar time interval in patients treated with sipuleucel-T in the three phase 3 clinical trials⁴⁶. using a single sample exact test for binary variables as defined above in the sample size justification. The same single sample test will be performed for IgM antibodies. The positive immune proportion for both IgG and IgM antibodies to PAP and to PA2024 with 95% confidence intervals will be used to summarize the results for each study arm. No adjustment for multiple comparisons will be made.

Exploratory analyses investigating the change in antibody response from baseline to week 20 when response is considered as a binary variable (positive or negative) will be investigated using the Mantel-Haenszel chi square statistic stratified by treatment arm. When the ELISA results are treated as continuous variables the change in each immune response will be analyzed using analysis of variance (ANOVA) methods.

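### The primary test compares IgG response to PAP or PA2024 with a 15% null taken from anti-PAP IgG alone in SipT-treated patients, so rejecting 15% does not show a response above SipT alone.

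*Combined protocol and SAP*

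**What the plan says.** Section 9.1.2 sets the endpoint: "Immune response is defined as an IgG antibody response to either PAP or PA2024 by study week 20", positive when the ELISA titer is above 1:400. Each arm of 27 is tested separately with a one-sample exact binomial test, two-sided 5%, for 40% against "a null hypothesis of 15% indicating lack of immune activity".

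The only basis offered for that figure is: "The null hypothesis of 15% is based off an observed anti-PAP IgG response rate of 17.7% seen at a similar time interval", in SipT-treated patients from three phase 3 trials. Section 9.3.1.2 repeats the basis and defines the primary analysis as "comparing the proportion of patients achieving an IgG immune response to PAP or PA2024 to the null hypothesis of 15" per cent. It also plans the same type of test for IgM, and a summary of IgG and IgM to each antigen separately with 95% confidence intervals.

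Other sections bear on how the result will be read:

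- Synopsis, Study Design: "All patients will be treated with the fixed treatment backbone of SipT (Q2 wks x 3"). There is no SipT-alone arm.
- Section 1, on PA2024: "The latter is the antigen used in producing SipT".
- Section 1.1: "We hypothesize that combining Sipuleucel T with ipilimumab will enhance the immunogenicity and clinical efficacy".
- Section 2.1: "Determine whether the timing of ipilimumab administration impacts PAP and PA2024-specific immune responses induced by SipT".

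**The concern.** A two-antigen endpoint is judged against a one-antigen rate. Response to PAP or PA2024 cannot be rarer than response to PAP alone. It may be more frequent, because PA2024 is the immunising antigen. The null is also set below the rate it was derived from, 15% against 17.7%. That gap is small; the mismatch of endpoints matters more, and its size is unknown.

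What is at stake is the meaning of a positive primary result. The benchmark was drawn from SipT-treated patients, and section 1.1 hypothesises that the combination enhances immunogenicity. A reader could easily take a rejection as evidence that ipilimumab added something. SipT alone might produce the same rejection, with a probability that the documents do not allow us to calculate.

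IgM has a related gap. Section 9.3.1.2 names the test but no IgM null, and the only null in the section comes from an IgG rate.

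**Working it through.** **Inputs.** From sections 9.1.2 and 9.3.1.2: n = 27 per arm, null 0.15, alternative 0.40, two-sided 5%, exact binomial, source rate 0.177 (anti-PAP IgG). No SipT-alone rate for PA2024, or for either antigen, is given.

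**Formula.** P(X ≥ r | p) = Σ from k = r to 27 of C(27,k) p^k (1−p)^(27−k).

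**1. The plan's own figure.** At p = 0.15, P(X ≥ 8) = 0.0398 and P(X ≥ 9) = 0.0138, so the smallest cut-off with an upper tail of at most 0.025 is 9. The summed exact two-sided p-value also gives 9. Power is P(X ≥ 9 | 0.40) = 0.816. The stated 81% with 27 per arm reproduces.

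**2. Lower bound for SipT alone.** P(PAP or PA2024) ≥ P(PAP). If assay, cut-off, time point and population match, the composite rate on SipT alone is at least 0.177.

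**3. Pass probability per arm when ipilimumab adds nothing.**

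| SipT-alone composite rate | P(X ≥ 9) | Status of the rate |
|---|---|---|
| 17.7% | 0.0375 | lower bound from the cited source |
| 20% | 0.0737 | assumption |
| 25% | 0.2141 | assumption |
| 30% | 0.4227 | assumption |

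At 17.7%, adding the lower rejection point gives P(X = 0) = 0.823^27 = 0.0052, so the two-sided size is 0.0375 + 0.0052 = 0.0427. The upper tail alone is above 0.025, and is 0.0375 / 0.0138 = 2.7 times its value at 15%.

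**4. Smallest passing result.** 9/27 = 33.3%, exact 95% CI 16.5% to 54.0%. The interval excludes 15% but includes 17.7%.

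**5. Re-sourced null, n = 27, alternative 40%.** Two conventions are in use: the summed exact p-value at 5%, or 2.5% in each tail.

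| Null | Summed: cut-off, power | 2.5% per tail: cut-off, power |
|---|---|---|
| 20% | 10, 0.691 | 11, 0.542 |
| 25% | 12, 0.387 | 12, 0.387 |

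**6. Anti-PAP IgG tested against 17.7%, n = 27.** The summed p-value at 9/27 is 0.0427, so the cut-off is 9. With 2.5% per tail the cut-off is 10, since P(X ≥ 10 | 0.177) = 0.0135.

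| True anti-PAP rate | Power, cut-off 9 | Power, cut-off 10 |
|---|---|---|
| 30% | 0.423 | 0.272 |
| 35% | 0.642 | 0.484 |
| 40% | 0.816 | 0.691 |

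Every anti-PAP responder is also a composite responder. An arm with 9 or 10 anti-PAP responders has therefore already met the composite cut-off of 9, and testing in that order costs no power.

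**The case against.** The strongest reply is that the protocol never claims superiority to SipT. It calls the trial non-comparative, and section 9.1.2 claims only immune activity. Section 1.3 says that a clinical advantage over SipT would need a randomised trial with overall survival as its endpoint, and section 2.1 is about timing. This stands as a description of the text: the over-reading is one that a reader might make, not one the plan writes. It does not rescue the label, because a rate below the cited SipT figure cannot mark inactivity in patients who all receive SipT.

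Second, no breach of the error rate is shown on the documents' own figures: 4.3% at 17.7% is inside 5%. This stands. PA2024 contains PAP, so overlap between the two responses may be large and the extra PA2024-only responders few.

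Third, PAP and PA2024 results are already to be reported separately with intervals. This helps, since anti-PAP IgG can be set beside 17.7%. No test or decision rule is attached to that comparison.

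Fourth, an in-trial reference may already be planned. Sections 7.1.1 and 9.3.1.2 name ELISA at baseline and week 20. Section 9.3.2.3, however, explores antibody and T cell agreement at every listed time point, including day 22, and Arm 2 gives blood that day before its first ipilimumab dose (section 6.1, footnotes b and d). This stands too; those sections need reconciling.

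**Conclusion.** The mismatch is explicit in sections 9.1.2 and 9.3.1.2. Rejecting 15% supports a response rate above 15% and nothing about SipT alone. The direction is certain only if the historical assay, titer cut-off, time point and population are comparable; the plan asserts only that the time interval is similar. The size is unknown. The pass probability without an ipilimumab effect is 3.8% at the documented lower bound. The 7%, 21% and 42% figures rest on assumed rates of 20%, 25% and 30%.

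A reader might infer three stronger points that the documents do not support:

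- That the type I error is inflated beyond 5%. This cannot be shown without a composite rate on SipT alone.
- That the sample size is wrong. The arithmetic for 15% against 40% is correct.
- That IgM is to be tested against 15%. The plan gives no IgM null, so this is a gap rather than a stated error.

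The point should be fixed, because it governs what the primary result can be said to mean.

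**What to change.** Keep the composite endpoint, since the primary objective names both antigens.

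1. If the source already cited gives a SipT-alone rate for IgG to PAP or PA2024 at a comparable titer and time, use it as the null and restate cut-off and power at n = 27. With the 40% alternative kept, power would be 69% or 54% at a 20% null, depending on the two-sided convention, and 39% at 25%.
2. If it does not, state in 9.1.2 and 9.3.1.2 that rejection supports only a rate above 15%, and remove the wording that equates 15% with inactivity. Add a test of anti-PAP IgG against 17.7% in each arm, after the composite test. State the two-sided convention (cut-off 9 or 10 of 27) and the limited power: 42% or 27% at a true 30%, 82% or 69% at 40%. The 40% target was set for the composite, so the anti-PAP rate may be lower. Say also that only the antigen is known to match, and that comparability of assay, cut-off and population is assumed.
3. Report IgM with confidence intervals and do not carry the 15% over to it.
4. Reconcile 7.1.1 and 9.3.1.2 with 9.3.2.3 on when antibodies are measured. Report Arm 2's day-22 pre-ipilimumab IgG to PAP and PA2024 as a descriptive SipT-only reference. It is a week-7 reading, not week 20, and imprecise: 7/27, for example, has a 95% CI of 11% to 46%.

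**Cost.** No extra patients: wording changes and a narrower conclusion. Item 4 needs at most 27 ELISA runs on blood already scheduled, and none if section 9.3.2.3 already implies them.

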9.2 Stopping Rules

9.2.1 Stopping Rules for Efficacy

There will be no interim analysis for efficacy due to the small sample size of each treatment arm. Although a secondary outcome measure is PSA decline, additional exploratory analyses will be performed to investigate the relationship between evidence of immune activation and clinical response to aid in designing future investigations.

